#### 9.2.2.6 Study Drug Compliance

Study drug compliance will be summarized based on the FAS.

Study drug compliance will be calculated as:  $100 \times [1 - (\text{total number of days of study drug interruption}) / (\text{duration of study drug exposure in days})]$ . A study drug interruption on a given day is defined as an interruption of any study drug dose or component on that day. In addition, a study drug interruption that continues through the end of the study participation (i.e., subject does not resume study drug before the end of the study participation) will not be included in the compliance calculation.

Study drug compliance will be summarized descriptively by the number of subjects (n), mean, SD, median, min, and max. It will also be summarized in categories: <80% and ≥80% using frequency tables.

### **9.2.2.7 Important Protocol Deviations**

An important protocol deviation (IPD) is a deviation that may significantly affect the completeness, accuracy, or reliability of the study data or that may significantly affect a subject's rights, safety, or well-being. A protocol deviation review team will categorize IPDs according to the Protocol Deviation Plan during the study.

IPDs will be provided in an individual subject data listing. A summary table of IPDs based on the FAS will also be provided.

## **9.3 Efficacy Analysis**

### **9.3.1 Efficacy Analysis for Part A**

Not applicable. There is no efficacy endpoint in Part A.

### **9.3.2 Efficacy Analysis for Part B**

There is no multiplicity adjustment; *P*-values provided for the secondary and other efficacy endpoints are considered nominal.

All efficacy analyses described in this section will be based on the FAS, unless otherwise specified. The analysis will include all available measurements through the last visit, including measurements after treatment discontinuation.

#### **9.3.2.1 Analysis of Primary Efficacy Variables**

Not applicable as efficacy is not a primary endpoint.

#### **9.3.2.2 Analysis of Secondary Efficacy Variables**

##### **9.3.2.2.1 Definition of Variables**

Sweat chloride (SwCl): the SwCl value for a given visit will be calculated as the mean of the non-missing sweat chloride measurements obtained on the left and right arms at that visit. If one of the two arm measurements at a time point is missing, the other will be used as the mean. A volume  $\geq 15$   $\mu\text{L}$  is required for an accurate determination of sweat chloride. Any results reported as having volume  $< 15$   $\mu\text{L}$  will be considered missing for analysis purposes. Any sweat chloride values reported as  $< 10$  mmol/L or  $> 160$  mmol/L will be considered missing for analysis purposes.

Lung clearance index (LCI): the LCI assessments are derived from  $\text{N}_2$ -multiple-breath washout (MBW) testing. Each MBW will be performed in multiple replicates for each visit and the final LCI value will be calculated from the technically acceptable washout replicates as graded and determined by a central reader. The following algorithm is used to derive the LCI values at each visit based on the multiple replicates:

- When there is only one acceptable replicate at the visit, the LCI values will not be calculated. The assessment for that subject at the corresponding visit will be missing.
- When there are 2 or more acceptable replicates at the visit, the mean of the values for the acceptable replicates will be calculated as the LCI value at the corresponding visit.

### 9.3.2.2.2 Analysis Method

#### Absolute change in sweat chloride from baseline through Week 24:

[figure not shown]
Absolute change from baseline in sweat chloride will be analyzed using a mixed-effects model for repeated measures (MMRM) approach based on the FAS. The MMRM will be used to estimate the within-group mean absolute change in sweat chloride through Week 24. The model will include absolute change from baseline in sweat chloride (including all measurements up to and including Week 24) as the dependent variable, and visit as the fixed effect, with baseline sweat chloride value and genotype group (F/F vs F/MF) as covariates. The model will be estimated using restricted maximum likelihood. Denominator degrees of freedom for the  $F$ -test of fixed effects will be estimated using the Kenward-Roger approximation. An unstructured covariance structure will be used to model the within-subject errors. If the model estimation does not converge, a compound symmetry covariance structure will be used instead. Conditional on the observed data and covariates, missing data will be assumed to be missing at random; consequently, no imputation of missing data will be performed.

[figure not shown]
The results obtained from the model will be the average treatment effect through Week 24, estimated using all post-baseline visits up to and including Week 24. The estimated mean change from baseline in sweat chloride through Week 24, along with the corresponding 2-sided 95% confidence interval (CI) and  $P$ -value, will be provided.

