**Number of Subjects** **Part A**

Approximately 14 subjects with F/F or F/MF genotypes are planned for enrollment. Subjects who participate in Part A may participate in Part B.

Part B

Approximately 70 subjects are planned for enrollment. At least 30 subjects with F/MF genotypes and at least 15 subjects with F/F genotypes are targeted for enrollment. At least 25 subjects should be between 2 and 3 years of age (inclusive).

Study Population **Part A**

Male and female CF subjects 2 through 5 years of age (inclusive) with F/MF or F/F genotypes. Subjects must weigh ≥ 14 kg at Day 1.

Part B

Male and female CF subjects 2 through 5 years of age (inclusive) who have at least 1 *F508del* mutation in the *CFTR* gene or an ELX/TEZ/IVA-responsive *CFTR* mutation. Subjects must weigh ≥ 10 kg at the Screening Visit.

Investigational Drug **Active substance:** ELX (VX-445)/TEZ (VX-661)/IVA (VX-770)

Activity: CFTR correctors (ELX and TEZ) and potentiator (IVA)

Strength and route of administration:

- **Parts A and B:** 100 mg ELX/50 mg TEZ/75 mg IVA FDC granules for oral administration **AND** 75 mg IVA granules for oral administration
- **Part B Only:** 80 mg ELX/40 mg TEZ/60 mg IVA FDC granules for oral administration **AND** 59.5 mg IVA granules for oral administration

Study Duration **Part A**

Excluding the Screening Period, subjects will participate in the study for up to 6 weeks (± 7 days)

Part B

Excluding the Screening Period, subjects will participate in the study for up to 28 weeks (± 7 days)

[figure not shown]
Study Design This is a Phase 3, 2-part (Parts A and B), multicenter study evaluating the safety, tolerability, PK, PD, and efficacy of ELX/TEZ/IVA in CF subjects 2 through 5 years of age (inclusive).

Part A

A schematic of the study design for Part A is provided below. Approximately 14 subjects (F/F or F/MF genotypes) will be enrolled. During the Treatment Period, subjects will be administered ELX/TEZ/IVA for approximately 15 days. Safety, tolerability, and available PK data from Part A will be reviewed by Vertex

to confirm or adjust the dose(s) chosen for Part B. Additional subjects may be enrolled as needed in Part A, based on emerging PK data, in order to provide sufficient information to select the dose(s) for Part B.

Figure 2-1 VX20-445-111 Part A Study Design

ELX: elexacaftor; IVA: ivacaftor; TEZ: tezacaftor

[figure not shown]

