8.1 Inclusion Criteria

1. Subject's legally appointed and authorized representative will sign and date an informed consent form (ICF).
2. Subjects (males and females), 2 through 5 years of age, inclusive, on the date of informed consent (and assent, as applicable).
3. In **Part A**, subjects must weigh ≥ 14 kg at Day 1. In **Part B**, subjects must weigh ≥ 10 kg at the Screening Visit.
4. Confirmed diagnosis of CF as determined by the investigator.
5. In **Part A**, subjects who are homozygous for *F508del* (F/F genotype) or heterozygous for *F508del* and an MF mutation that is not responsive to IVA and TEZ/IVA (F/MF genotypes; [Appendix A](#)). In **Part B**, subjects who have at least 1 *F508del* mutation in the *CFTR* gene or an ELX/TEZ/IVA-responsive *CFTR* mutation ([Appendix B](#)).
 - Genotype should be confirmed at the Screening Visit. This assessment does not need to be repeated for confirmed subjects in Part A who wish to participate in Part B.
 - If the screening *CFTR* genotype result is not received before the first dose of study drug, a previous *CFTR* genotype laboratory report may be used to establish eligibility.

- Subjects who have been enrolled and whose screening genotype does not confirm study eligibility must be discontinued from the study (Section 9.9).
6. Subjects with stable CF disease at the start of the Treatment Period as deemed by the investigator.
 7. Subjects who are willing to remain on a stable CF medication regimen (other than *CFTR* modulators) through Day 15 (**Part A**) or through Week 24 (**Part B**) or, if applicable, through the Safety Follow-up Visit.
 8. As judged by the investigator, the parent or legal guardian must be able to understand protocol requirements, restrictions, and instructions and the parent or legal guardian should be able to ensure that the subject will comply with and is likely to complete the study as planned.

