12.3.3.2 Analysis of Secondary Efficacy and Pharmacodynamic Endpoints

A summary of observed values and change from baseline will be provided for all secondary efficacy endpoints based on the FAS in Part B.

- **Absolute change in SwCl from baseline through Week 24**

Absolute change from baseline in SwCl will be analyzed using a mixed-effects model for repeated measures (MMRM) approach based on the FAS. The MMRM will be used to estimate the mean absolute change in SwCl through Week 24. The model will include absolute change from baseline in SwCl as the dependent variable, and with visit, baseline SwCl value, and genotype group as covariates. Data obtained from Week 4, Week 12, and Week 24 Visits will be included in the model. An unstructured covariance structure will be used to model the within-subject variations.

[figure not shown]
The primary results obtained from the model will be the average treatment effect through Week 24. The estimated mean change from baseline in SwCl through Week 24, along with the corresponding 95% CI and 2-sided *P* value will be provided. The treatment effect at each post-baseline visit, obtained from the model, will be provided as well.

- **Absolute change in LCI_{2.5} from baseline through Week 24**

Analysis of this endpoint will be based on an MMRM model that is similar to the analysis of absolute change from baseline in SwCl through Week 24, with the baseline LCI_{2.5} value included as a covariate instead of baseline SwCl.

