#### Part B

A schematic of the study design for Part B is provided in [Figure 7-2](#). Part B will initiate after available data from Part A has been reviewed by Vertex and the Part B dose(s) has been confirmed or adjusted. Part B will enroll approximately 70 subjects, of which at least 30 subjects will have F/MF genotypes and at least 15 subjects with the F/F genotype. At least 25 subjects should be between 2 and 3 years of age (inclusive). During the Treatment Period, subjects will be administered ELX/TEZ/IVA ([Table 7-1](#)) for approximately 24 weeks.

Subjects who are eligible will be offered the opportunity to enroll in an open-label extension (OLE) safety study.

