#### 8.3 Full Analysis Set

The **Full Analysis Set (FAS)** will include all subjects who are enrolled and carry the intended *CFTR* allele mutation and receive at least 1 dose of study drug. The FAS will be used to summarize subject demographics and baseline characteristics, and for analyses of all efficacy and PD endpoints, unless otherwise specified.

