### **9.2.1.2 Demographics and Baseline Characteristics**

[figure not shown]
Demographics and baseline characteristics will be summarized based on the FAS.

Demographic data will include the following:

- Age at baseline (in years)
- Sex (male, female)
- Ethnicity (Hispanic or Latino, not Hispanic or Latino, and not collected per local regulations)
- Race (White, Black or African American, Asian, American Indian or Alaska Native, Native Hawaiian or Other Pacific Islander, Other, and not collected per local regulations)

Baseline characteristics will include the following:

- CFTR genotype group (F/F, F/MF)

In addition, the following data listings will also be provided:

- Informed consent/assent;
- Inclusion/Exclusion criteria violation for subjects with any such violations.

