### **9.2.2.2 Demographics and Baseline Characteristics**

Demographics and baseline characteristics will be summarized based on the FAS.

[figure not shown]
Demographic data will include the following:

- Age at baseline (in years)
- Age group at screening ( $\geq 2$  to  $<3$ ,  $\geq 3$  to  $<4$ ,  $\geq 4$  to  $<5$ , and  $\geq 5$  to  $<6$  years)
- Sex (male, female)
- Ethnicity (Hispanic or Latino, not Hispanic or Latino, and not collected per local regulations)
- Race (White, Black or African American, Asian, American Indian or Alaska Native, Native Hawaiian or Other Pacific Islander, Other, and not collected per local regulations)
- Geographic region (North America, Europe [including Australia])

Baseline characteristics will include the following:

- CFTR genotype group (F/F, F/MF, Other)
- Weight group (<14 kg, and ≥14 kg)

Disease characteristics will include the following:

- Sweat chloride at baseline (continuous)
- LCI2.5 at baseline (continuous)
- Prior use of CFTR modulator (Yes, No)
- Prior use of dornase alfa (Yes, No)
- Prior use of azithromycin (Yes, No)
- Prior use of inhaled antibiotic (Yes, No)
- Prior use of any bronchodilator (Yes, No)
- Prior use of any inhaled bronchodilator (Yes, No)
- Prior use of any inhaled hypertonic saline (Yes, No)
- Infection with *Pseudomonas aeruginosa* within 2 years prior to screening (Positive, Negative)

In addition, the following data listings will also be provided:

- Informed consent/assent;
- Inclusion/Exclusion criteria violation for subjects with any such violations.

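### The Part B sweat chloride and LCI2.5 models code genotype as F/F vs F/MF, leaving no level for children of other eligible genotypes in the Full Analysis Set

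*SAP*

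**What the plan says.** SAP 9.3.2.2.2 analyses change in sweat chloride with an MMRM on the FAS, with visit as a fixed effect and "with baseline sweat chloride value and genotype group (F/F vs F/MF) as covariates". The LCI2.5 model in the same section is described as similar. Only the baseline covariate is named as changed, and the set is narrowed to FAS children who did at least one multiple-breath washout.

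Protocol 8.1 admits to Part B "subjects who have at least 1 *F508del* mutation in the *CFTR* gene or an ELX/TEZ/IVA-responsive *CFTR* mutation". SAP 8.3 places no F/F or F/MF limit on the FAS and states: "The FAS will be used to summarize subject demographics and baseline characteristics, and for analyses of all efficacy and PD endpoints". The Part B baseline table (SAP 9.2.2.2), also on the FAS, lists "CFTR genotype group (F/F, F/MF, Other" as its groups. The Part A table (SAP 9.2.1.2) lists only "CFTR genotype group (F/F, F/MF".

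Protocol 12.3.3.2 describes the model "with visit, baseline SwCl value, and genotype group as covariates", without naming the levels.

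**The concern.** For the same part and the same analysis set, the SAP has three genotype groups in the baseline table and two in the efficacy models. Two groups fit Part A, where eligibility was limited to F/F and F/MF. They do not cover Part B, which also admits, for example, a child with one F508del allele and a second allele that is not minimal-function, or a child with no F508del allele but a mutation listed in Protocol Appendix B.

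If such children contribute data and are dropped, the two estimates describe F/F and F/MF children only, although they are labelled as FAS results. The genotypes left out would be the ones that Part B eligibility added. The coding would be settled at the programming stage of an open-label, single-arm study, where it ought to be fixed in writing beforehand.

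**Working it through.** **Plan's own figures.** The plan gives no power, SD or effect size for sweat chloride or LCI2.5. Its only Part B sample-size figures are the probabilities of seeing at least one subject with an AE, 1 − (1 − θ)^n. These reproduce: 94.34% and 99.73% for n = 56, and 96.05% and 99.87% for n = 63, against the stated 94.3%, 99.7%, 96.1% and 99.9%. The genotype coding does not affect them.

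**What each coding does.** In a dummy data set of 70 (15 F/F, 45 F/MF, 10 Other):

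- a two-level class variable with Other treated as missing uses 60 records;
- an indicator for F/F against everyone else uses 70, and silently pools Other with F/MF;
- a three-level variable uses 70.

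The SAP sentence can therefore be programmed in ways that answer different questions.

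**Room for Other children.** The protocol synopsis says: "At least 30 subjects with F/MF genotypes and at least 15 subjects with F/F genotypes are targeted for enrollment". The total is about 70 (SAP 7.1). So 70 − 30 − 15 = 25, a range of 0 to about 25. The limit is soft because the minimums are targets.

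**Precision.** With equal variances and observed-proportion weights, dropping k of 70 multiplies the CI width by about √(70/(70 − k)).

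**Estimate.** With both versions of the model averaged at observed proportions, the shift is (k/70) × d. Here d is the difference in mean change between Other children and the rest. The documents give no value for d, so 5, 10 and 20 mmol/L are assumptions.

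| Other, k | Share k/70 | CI width ratio | Shift, d = 5 | Shift, d = 10 | Shift, d = 20 |
|---|---|---|---|---|---|
| 5 | 7.1% | 1.038 | 0.36 | 0.71 | 1.43 |
| 10 | 14.3% | 1.080 | 0.71 | 1.43 | 2.86 |
| 15 | 21.4% | 1.128 | 1.07 | 2.14 | 4.29 |
| 25 | 35.7% | 1.247 | 1.79 | 3.57 | 7.14 |

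Shifts are in mmol/L.

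**Simulation check.** This used 2000 runs per setting, a subject-mean ANCOVA with a baseline covariate, complete data, an assumed SD of 15 and observed weights. It compared the two-level model without Other children with the three-level model, for d = 5, 10 and 20.

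- 45 F/MF, 20 F/F, 5 Other: shifts of 0.34, 0.73 and 1.43; SE ratio 1.04.
- 30 F/MF, 15 F/F, 25 Other: shifts of 1.75, 3.57 and 7.12; SE ratio 1.25.

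**LCI2.5.** The effect cannot be computed, because the number of children with washout data is not given.

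**Why the weights need stating once a third level is added.** In SD units, at one visit and ignoring baseline, the SE of the overall mean is 1/√70 = 0.120 with observed weights. With equal weights it is (1/3)√(Σ 1/n_g):

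- 45/20/5 (F/MF, F/F, Other): 0.174
- 45/23/2: 0.251
- 46/23/1: 0.344

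Equal weighting would give a single Other child one third of the estimate.

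**The case against.** The strongest reply is that dropping records is only one reading. SAP 9.3.2 bases efficacy on the FAS and says all available measurements are included. A programmer who used the baseline-table genotype variable as the class variable would get three levels and lose nobody. That is a fair account of what may have been intended, but it contradicts the levels actually written for the model, so the text still has to be corrected. Nor is a deliberate F/F and F/MF analysis a natural reading: where the SAP narrows the set, as for children with washout data, it says so.

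The size of the effect depends on unknowns. The number of Other children is not stated and may be zero, and 25 is a ceiling rather than an expectation. The mmol/L differences and the SD of 15 are assumptions, and the simulation mainly confirms the algebra. The SAP names no LS-mean weights, so the shifts hold only under observed weighting; with equal weights in both versions the shift would be d/3 whatever k is. All of this stands, and it is why the size is given as a range.

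The weighting sentence is also a choice in its own right and can matter with no Other child present. For an illustrative split of 45 F/MF and 25 F/F, moving from equal to observed weights shifts the estimate by 45/70 − 1/2 = 0.143 times the difference between the groups. That is correct. But observed weights contradict nothing in the SAP and suit an FAS mean, and the correction to the levels stands without them.

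Finally, parts of SAP 9.3 are redacted, and a genotype rule there cannot be ruled out. The visible covariate definition would still disagree with the baseline table.

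**Conclusion.** The concern holds. The genotype term as written does not cover the set on which both models are said to be based, and no visible text resolves this. If no Other child contributes data, the models run as written and nothing changes. If some do and are dropped, the loss of precision is small to moderate (about 4% to 25% in CI width for 5 to 25 children), and the shift in the sweat chloride estimate depends on a difference the documents do not give.

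The consequence is limited. Both endpoints are secondary, P values are nominal (SAP 9.3.2), the primary safety analysis does not use the term, and the by-visit descriptive summaries of sweat chloride and LCI2.5 do not use it either. It should be fixed, but it does not threaten the study's primary conclusion. Confidence is high that the specification is inconsistent; the size of the effect cannot be known from the documents.

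**What to change.** In SAP 9.3.2.2.2, for both models, give the covariate as genotype group with levels F/F, F/MF and Other, as in SAP 9.2.2.2.

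Add one sentence stating that LS means are evaluated at the observed genotype proportions of the subjects contributing to each model, that is, those with a non-missing baseline and at least one non-missing post-baseline value for that endpoint, each counted once. A level with no contributing subject then drops out. This can happen even when an Other child is in the FAS, because SAP 9.3.2.2.1 sets some sweat chloride and LCI results to missing.

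If the sponsor means to analyse F/F and F/MF children only, the SAP should say that both models are restricted to those groups and how Other children are reported. A named pooling rule would also remove the ambiguity, provided it is written down.

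The cost is two SAP sentences. No new data are needed, and no protocol amendment, since Protocol 12.3.3.2 leaves the levels open. The one drawback is an extra model parameter that may rest on few children.

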#### Absolute change in LCI2.5 from baseline through Week 24:

Analysis of this variable will be based on an MMRM similar to the analysis of the absolute change in sweat chloride from baseline through Week 24, with the baseline LCI2.5 included as a covariate instead of baseline sweat chloride. The analysis will be based on subjects in the FAS who have performed MBW as an assessment at least once.

To better assess the longitudinal profile of sweat chloride and LCI2.5 with repeated measures up to Week 24, the LS mean (SE) of the change from baseline at each post-baseline visit along with the 95% CI will be estimated from the corresponding MMRM. The LS mean (SE) at each visit will also be plotted. In addition, the post-baseline raw values and the absolute change from baseline at each post-baseline visit will be summarized descriptively (n, mean, SD, median, minimum, and maximum).

[figure not shown]

#### **9.3.2.4 Sensitivity Analysis**

Not applicable because the primary endpoints are safety and tolerability assessments.

### **9.4 Safety Analysis**

#### **9.4.1 Safety Analysis for Part A**

Safety is one of the primary objectives of Part A. All safety analyses will be conducted based on data from the TE period in the Safety Set.

The following safety and tolerability endpoints will be assessed:

- Treatment-emergent adverse events (TEAEs)
- Clinical laboratory values
- Standard 12-lead ECGs
- Vital signs

- Pulse oximetry

Only descriptive analysis of safety will be performed, and no statistical testing will be performed.

